#### **2 OBJECTIVES OF THE STUDY**

#### 2.1 Research objectives and hypotheses

In the Medical Admissions Units/Wards of the University Hospitals of Leicester, to:

1. Determine the diagnostic accuracy (sensitivity, specificity, positive and negative predictive values) of rapid molecular and near patient diagnostic tests for influenza, RSV and *S. pneumoniae* infections in comparison to traditional laboratory culture.

The increased diagnostic accuracy of rapid molecular and near patient tests over traditional laboratory methods improves patient management through better use of antimicrobials and isolation facilities. Rapid molecular and near patient diagnostic tests for influenza, RSV and S. pneumoniae infections are more cost-effective than traditional laboratory diagnostic tests.

2. Assess the potential benefits of ease of use, and speed of rapid molecular and near patient diagnostic tests for influenza, RSV and *S. pneumoniae* infections, in comparison to traditional laboratory culture.

Rapid molecular and near patient diagnostic tests for influenza, RSV and S. pneumoniae infections provide benefits in terms of (a) ease of use, and (b) more rapid results, in comparison to traditional laboratory culture.

3. Determine whether rapid molecular and near patient diagnostic tests for influenza, RSV and *S. pneumoniae* infections have any impact on prescribing.

Rapid molecular and near patient diagnostic tests for influenza, RSV and S. pneumoniae infections result in earlier use of narrow-spectrum antimicrobial therapy; and/or an earlier switch from intravenous to oral therapy; and/or earlier discontinuation of antibiotics in patients infected with influenza and RSV - in comparison to traditional laboratory culture

4. Determine whether rapid molecular and near patient diagnostic tests for influenza, RSV and *S. pneumoniae* infections allow more appropriate use of isolation facilities, in comparison to traditional laboratory culture.

Rapid detection of influenza and RSV by rapid molecular and near patient diagnostic tests leads to the appropriate isolation of patients, but only in hospitals/wards with an adequate provision of cubicles.

5. Compare the costs of performing rapid molecular and near patient diagnostic tests for influenza, RSV and *S. pneumoniae* infections, in comparison to traditional laboratory culture.

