#### 6.1.10 Quality of Life assessment

All patients will be assessed by the EuroQol (Appendix I) on admission, (by proxy if they are incapable of completing the self-administered questionnaire or providing a verbal response) and the findings entered into the CRF.

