#### 6.1.13 Randomisation and Trial Identification Numbers

Patients in each centre will be randomly allocated, using computer generated randomisation codes stratified by centre, to one of three diagnostic study groups:

Group 1: Rapid near patient diagnostic tests (influenza and pneumococcus),

Group 2: Rapid molecular tests (influenza & RSV), plus laboratory pneumococcal antigen testing, and Group 3: Traditional 'laboratory culture' (influenza, RSV, and *S. pneumoniae*)]

The randomisation code (i.e., whether in Group 1, 2, or 3) will be included in sequentially numbered study packs that will be stored at each hospital (Leicester Royal Infirmary, Glenfield Hospital, and Leicester General Hospital). The Packs will be labelled as follows:

1-0001, etc, (Leicester Royal Infirmary site One)

**2**-0001, etc, (Glenfield Hospital siteTwo)

**3**-0001, etc, (Leicester General Hospital site Three) which correspond to the Trial Identification Numbers allocated to participants at each study site.

The randomisation codes will be generated by the Department of Health Sciences, University of Leicester. The randomisation code will not be known by the Study Nurse until after the patient has signed the Patient Informed Consent Form. Only then will the study pack containing details of randomisation be opened.

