#### 7.6 Statistical analysis

All analyses for both process and clinical outcomes will be based on Intention to Treat (ITT) analyses.

Impact of test result on prescribing The time to prescription of `narrow spectrum', `oral antibiotics' or `no antibiotics' between the three groups will be assessed using survival analysis techniques, whilst the use of neuraminidase inhibitors in those with influenza will be assessed using  $\chi^2$  tests, together with 95% CIs. Further analyses to allow for potential differences in patient demographics and baseline clinical characteristics between the three diagnostic test groups, and not allowed by stratification, will make use of cox proportional hazards regression modelling in the case of time to appropriate prescribing and logistic regression techniques in the case of neuraminidase inhibitors.

*Length of hospital stay* Length of hospital stay in the three diagnostic groups will initially be compared using non-parametric methods. Further analyses to allow for potential differences in patient demographics and baseline clinical characteristics between the three diagnostic test groups, and not allowed by stratification, will make use of generalised linear models in order to accommodate any skewness in the data.

*Mortality rates* Mortality rates between the three diagnostic testing groups will be compared by means of a Log-Rank Test and Kaplan-Meier survival curves. Adjustment for potential differences in patient demographics and baseline clinical characteristics between the three diagnostic test groups, and not allowed by stratification, will make use of Cox proportional hazards regression methods.

*Diagnostic accuracy* Sensitivity, specificity, positive predictive value of molecular and near patient diagnostic tests in comparison to traditional laboratory methods will be calculated together with 95% CIs. Heterogeneity in the sensitivity and specificity with respect to patient demographics and baseline clinical characteristics will be explored as secondary analyses using patient defined sub-groups.

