Admission to intensive care The proportions of patients in the three groups who are admitted to intensive care within the first 10 days of admission will be compared using  $\chi^2$  tests, together with 95% CIs. Further analyses to allow for potential differences in patient demographics and baseline clinical characteristics between the three diagnostic test groups, and not allowed by stratification, will make use of logistic regression techniques.

*Ventilatory support* The proportions of patients in the three groups who receive ventilatory support within the first 10 days of admission will be compared using  $\chi^2$  tests, together with 95% CIs. Further analyses to allow for potential differences in patient demographics and baseline clinical characteristics between the three diagnostic test groups, and not allowed by stratification, will make use of logistic regression techniques.

Appropriate use of isolation facilities In patients with confirmed influenza or RSV the time taken from admission to the MAU to admission to a single room (isolation cubicle) will be compared between the three diagnostic groups by means of a Log-Rank Test and Kaplan-Meier survival curves. Adjustment for potential differences in patient demographics and baseline clinical characteristics between the three diagnostic test groups, and not allowed by stratification, will make use of Cox proportional hazards regression methods.

*Quality of Life (EQ-5D)* Quality of life in the three diagnostic groups will initially be compared using non-parametric methods. Further analyses to allow for potential differences in patient demographics and baseline clinical characteristics between the three diagnostic test groups, and not allowed by stratification, will make use of generalised linear models in order to accommodate any skewness in the data.

*Speed of Tests* Time taken to receive test results in the three diagnostic groups will initially be compared using non-parametric methods. Further analyses to allow for potential differences in patient demographics and baseline clinical characteristics between the three diagnostic test groups, and not allowed by stratification, will make use of generalised linear models in order to accommodate any skewness in the data.

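### Allocation is stratified by centre, but the first comparisons in section 7.6 are named without centre and without admission EuroQol, which gives away precision

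*Protocol*

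**What the plan says.** Protocol section 6.1.13 (and the synopsis) allocates patients to the three groups "using computer generated randomisation codes stratified by centre". The centres are the three Leicester hospitals.

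Section 7.6, repeated in the synopsis, gives most outcomes a simple first comparison and then a model:

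- **Isolation and mortality:** log-rank test, then Cox regression. For isolation, times "will be compared between the three diagnostic groups by means of a Log-Rank Test and Kaplan-Meier survival curves".
- **Neuraminidase inhibitor use, intensive care and ventilatory support:** chi-square tests, then logistic regression.
- **Length of stay, quality of life and speed of tests:** rank-type methods, then generalised linear models. For example, "Quality of life in the three diagnostic groups will initially be compared using non-parametric methods".

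Centre is named in none of these. The models are introduced as dealing with possible differences in demographics and baseline clinical characteristics "between the three diagnostic test groups, and not allowed by stratification, will make use of" the regression method concerned.

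On quality of life, section 6.1.10 states: "All patients will be assessed by the EuroQol (Appendix I) on admission". Section 6.2.9 repeats the measurement on days 7 and 28. The quality-of-life paragraph in 7.6 does not name the admission score.

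Hypothesis 4 in section 2.1 says that rapid detection "leads to the appropriate isolation of patients, but only in hospitals/wards with an adequate provision of cubicles". The protocol therefore expects isolation to depend on where the patient is nursed.

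**The concern.** Stratified allocation balances the groups within each hospital, so variation between hospitals drops out of the true sampling variance of a group difference. An analysis that leaves centre out still counts that variation in its standard error. If centre is prognostic, the intervals are then too wide and the tests reject less often than their nominal level. The scoping phrase in 7.6 makes this more likely, because it suggests that a factor used in stratification has already been dealt with. Balancing a factor in the design does not account for it in the analysis.

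Isolation is the outcome most exposed. Single-room provision is a property of hospital and ward, the analysis is restricted to patients with influenza or RSV, and isolation is one of only two clinical endpoints with a power statement (section 7.4).

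For quality of life the same argument applies to the admission score. It is likely to predict the follow-up score and is already collected, but the first comparison does not use it. A chance difference at admission then stays in that comparison as noise and can carry into the QALY estimate.

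**Working it through.** **Inputs from the protocol.** N = 2752 elderly patients, 20% dropout, three groups; length-of-stay difference 1 day, SD 6 days, 5% level, power above 80%; isolation 5% versus 15%; influenza 10% and RSV 5% of patients. Sidedness is not stated; two-sided tests are assumed.

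**Inputs assumed.** The protocol gives no isolation rates by hospital, no share of variance due to centre and no EuroQol correlation. All such values below are assumptions, shown as ranges.

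**1. The protocol's own figure.** Evaluable patients per group: 2752 × 0.8 / 3 = 733.9. Power = Φ(Δ / (SD√(2/n)) − z), with 1 / (6 × √(2/733.9)) = 3.19.

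- Level 0.05/2 (two comparisons with Group 3): z = 2.24, power 82.9%.
- Level 0.05/3 (all pairs): z = 2.39, power 78.8%.

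The stated power is reproduced with the level halved and is missed narrowly with the level divided by three.

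**2. Centre in a continuous outcome.** If centre explains a share R² of the variance, the residual SD is 6√(1 − R²). Starting from 82.9%, including centre gives:

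| R² | Power |
|---|---|
| 1% | 83.3% |
| 5% | 84.9% |
| 10% | 86.9% |

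The gain is 0.4 to 4 points.

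**3. Centre in the isolation log-rank test.** Patients with influenza or RSV per group: 733.9 × 0.15 ≈ 110. Simulation: 4000 runs, three equal centres, 120 hours of follow-up, global 2-df test at 5%, Groups 1 and 2 sharing one hazard ratio against Group 3. A change from 5% to 15% corresponds to a hazard ratio of ln(0.85)/ln(0.95) = 3.17; 1.5 was used where base rates are high.

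| Group 3 isolation by centre | Hazard ratio | Power, unstratified | Power, stratified | Null rejection, unstratified | Null rejection, stratified |
|---|---|---|---|---|---|
| 5/5/5% | 3.17 | 71.6% | 71.7% | 4.6% | 4.7% |
| 2/5/8% | 3.17 | 69.1% | 70.3% | 4.6% | 4.7% |
| 20/40/60% | 1.5 | 44.0% | 52.5% | 3.2% | 4.8% |
| 10/40/80% | 1.5 | 25.7% | 56.2% | 1.0% | 5.1% |

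The loss is nil when centres are alike, about 1 point near the planning rate, and 8 to 30 points when hospitals differ strongly. In the last two rows the unstratified test is clearly conservative. These runs compare the two tests at 5%; they do not re-derive the protocol's isolation power, which is stated at 1%.

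**4. Isolation as a proportion** (endpoint 4(b) in section 7.5.1). The standard error is inflated by √[P(1 − P) / Σw p(1 − p)], where p and w are the rate and share of each centre and P is the overall rate.

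| Rates by centre | Shares | Calculation | Inflation | Sample wasted |
|---|---|---|---|---|
| 3/10/20% | 0.5/0.3/0.2 | √(0.07778/0.07355) | 1.028 | 5% |
| 2/5/30% | equal | √(0.10812/0.09237) | 1.082 | 15% |
| 5/20/50% | 0.5/0.3/0.2 | √(0.15078/0.12175) | 1.113 | 19% |

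**5. Admission EuroQol as covariate.** The variance factor is 1 − r², with r the correlation between admission and follow-up scores. For r = 0.3, 0.5 and 0.6 it is 0.91, 0.75 and 0.64, so variance falls by 9%, 25% and 36%. For a comparison with the same standardised difference as length of stay, 82.9% power becomes 86.5% at r = 0.3 and 92.6% at r = 0.5.

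**The case against.** The strongest reply is that this is detail for a statistical analysis plan. Section 7.6 never says that the tests are unstratified; a stratified log-rank test is still a log-rank test, and van Elteren's test is non-parametric. The scoping phrase says which further factors the models are for and does not clearly exclude centre. This stands in part: the wording permits a centre-stratified analysis. It does not ask for one, however, and its most natural reading points the other way.

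On quality of life, the next sentence of 7.6 provides a model with baseline clinical characteristics, and the synopsis lists the quality-of-life assessment among the baseline items. Admission EuroQol could therefore enter that model. This also stands, and it limits the point to the first comparison and to the lack of any requirement in the second.

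On size, the large losses need isolation rates well above the 5% used for planning and strong contrasts between hospitals of one Trust. This stands too: near the planning rate the loss is about 1 point.

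A reader might also infer from the text that Hypothesis 4 cannot be answered, or that covariates will be picked from observed imbalances. The documents support neither. Ward location and isolation status are recorded, so results can be described by hospital, and 7.6 speaks of possible differences without giving any selection rule based on the data.

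**Conclusion.** The point holds as a loss of precision in the stated methods. The design stratifies by centre, the first comparisons are named without it, and the models are scoped in a way that suggests it can be left out. The first quality-of-life comparison does not use a baseline score that is already collected, and the later model does not require it.

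A reader might take this as a threat to validity, but it is not one. Omitting centre after stratified allocation does not bias the comparison or raise type I error; any error is on the conservative side.

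The size depends wholly on assumed values. For centre it is negligible if the hospitals are alike, about 1 power point for isolation at low rates, and 8 to 30 points if isolation differs strongly by hospital. For EuroQol, correlations of 0.3 to 0.6 correspond to a 9 to 36% reduction in variance. The change is worth making because it costs nothing and because the protocol itself expects isolation to vary with cubicle provision.

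**What to change.** In section 7.6 and the matching synopsis text:

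- Name centre-stratified first comparisons: stratified log-rank for times, Cochran-Mantel-Haenszel for proportions, and van Elteren for length of stay, quality of life and speed of tests.
- Include centre in the Cox, logistic and generalised linear models, and reword the scoping phrase so that it cannot be read as leaving centre out. Where events are sparse, stratify instead of adding terms: at the mortality of about 2.5% quoted in section 1.5, the 249 expected pneumococcal cases would give about 6 deaths (0.025 × 249) over three groups.
- Make the main day 7 and day 28 EuroQol comparison, and the QALY comparison, one adjusted for admission EuroQol and centre, with a stated rule for proxy and missing admission scores.
- Report isolation by centre as exploratory, low-power evidence on Hypothesis 4. With about 110 infected patients per group over three hospitals, each cell holds about 37 if the split is equal. Centre is also only a proxy, because the hypothesis concerns cubicle provision by hospital and ward, so this does not test it fully.

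The cost is wording only. Centre is part of every trial identification number, and EuroQol on admission and isolation status are already recorded.

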#### Cost Data

Cost data will be analysed using parametric and non-parametric statistical methods which explicitly allow for the censoring of (indirect & total) costs at 28 days, i.e. for those patients who are not discharged from hospital within 28 days, and thus allow an unbiased assessment of potential cost differences between the three diagnostic groups. Estimation of the cost distribution over longer timescales will make use of extrapolation techniques using time of discharge obtained from hospital information systems.

#### 7.7 Data management

CRF data will be entered into a research system for collecting, managing, and reviewing clinical trial data. The data will be maintained on a secure server at the University Hospitals of Leicester. Statistical and health economic analyses will be done on anonymised data transferred from the UHL server to the Department of Health Sciences, University of Leicester. Throughout the study's life cycle, a history of users and corresponding access rights will be maintained and documented.

#### 8 LABORATORY TESTS

#### 8.1 Specimen collection

Instructions for the collection of specimens are outlined in detail elsewhere (See 6.1.14).

#### 8.2 Specimen transport and processing

Instructions for the transport and processing of specimens are provided elsewhere (See 6.1.14).

#### 9 SCHEDULING OF THE STUDY

#### Year 1: 1 June 2005 - 31 May 2006

1. **June** – **August 2005:** Purchase computers, refrigerators, & diagnostic kits and other consumables for first year; appoint three research nurses; post-doctoral RA; and MLSO; set up committees for

trial management and independent review & initiate work programme; generate randomisation code; produce and print CRF and develop trial database.

- 2. July August 2005: Transfer of PCR Technology to Leicester; review SOP's in UHL Virology Laboratory.
- 3. August 2005: Pilot study of CRFs, patient recruitment, specimen handling, etc, and refinements as necessary.
- 1 September 2005 30 June 2006: Year 1 clinical trial; Trial Management Committee to review progress after 4 weeks of operation & continue with ongoing audit of patient recruitment, data entry into CRFs.
- 5. **December 2005 & March 2006:** Independent Data Monitoring Committee to hold their 1st & 2nd meetings and decide future meetings.
- 6. Nov 2005, Jan 2006, Mar 2006, May 2006: Review by Trial steering Committee of progress of Year 1 clinical trial.

#### Year 2: I June 2006 - 31 May 2007

- June August 2006: Carry out PCR, serology, & analysis of stored urine specimens; Audit and analysis of Year 1 data: purchase diagnostic kits and other consumables for second year. Prepare Year 1 analytical report.
- 2. **1 September 14 December 2006:** Collate and analyse all diagnostic data from Year 1, including serological data; Prepare Year 1 analytical report by 14 December 2006.
- 3. **1 September 2006 30 June 2007:** Year 2 clinical trial; continue with ongoing audit of patient recruitment, data entry into CRFs.
- 4. February 31 May 2007 Carry out 'Ease of test' study during February-May.
- 5. Nov 2006, Jan 2007, Mar 2007, May 2007: Review by Trial steering Committee of progress of Year 1 and 2 data.

#### Year 3: I June 2007 - 31 May 2008

- 1. Jun July 2007: Analyse data of 'Ease of test' and report findings
- 2. May Aug 2007: Carry out PCR, serology, & analysis of stored urine specimens; Audit and analysis of Year 2 data: purchase diagnostic kits and other consumables for third year.
- 3. **June-Aug 2007:** Audit and analysis of Year 2 data: Determine the diagnostic accuracy of rapid molecular and near patient diagnostic tests; carry out PCR, serology, & analysis of stored urine specimens from year 2 study.
- 4. **1 Sept 14 Dec 2007:** Collate and analyse all diagnostic data from Years 1 & 2, including serological data; prepare combined year 1 and year 2 analytical report by 14 December 2007.
- 5. 1st Sept 2007 to June 2008.: Year 3 clinical trial; continue with ongoing audit of patient recruitment, data entry into CRFs.
- 1 Jan 31 Mar 2008: Carry out PCR, serology, & analysis of stored urine specimens from year 2 study; collate all data in preparation for analyses.
- 1 Apr 31 May 2008: Data analysis (Years 1-3 combined); preparation of draft 3-year report. Consider publication strategy.

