Sponsor	NHS R&D National Coordinating Centre for Health Technology Wessex Institute for Health Research & development [name]
	[contact] [contact]
Date	26/11/2007 Version 6

Information contained in this document is the property of Leicester University and is therefore provided to you in confidence for review by you, your staff, or an applicable ethics committee. This information may not be disclosed to others without written approval from the Principal Investigator, except to the extent necessary to obtain informed consent from those persons entering the study. This document may not be reproduced, stored in a retrieval system or transmitted in any form or by any means without prior authorisation from the Principal Investigator. This document must be returned to the Principal Investigator upon request.

	PROTOCOL SYNOPSIS
Title	Randomised controlled trial to evaluate impact of diagnostic testing for influenza, respiratory syncytial virus and Streptococcus pneumoniae infection on the management of acute admissions in the elderly and high risk 18-64-year-olds.
Sponsor	NHS R&D National Coordinating Centre for Health Technology Assessment
Study population	Male or female elderly ( $\geq$ 65 years old) patients, Male or female patients aged $\geq$ 18 years with underlying heart or lung disease including asthma , or pneumonia / influenza type symptoms.
Study setting	Medical Admissions Units in the University Hospitals of Leicester NHS Trust (Leicester Royal Infirmary, Glenfield Hospital, Leicester General Hospital).
Duration	August 1 2005- July 31 2008 (36m). Patient enrolment will occur during September 1 2005 to June 30 2006; September 1 2006 to June 30 2007; & September 1 2007 to June 30 2008 All patients will be followed-up for 28 days.
Rationale	The purpose of this study is to determine the diagnostic accuracy and clinical- and cost-effectiveness of rapid molecular and near patient diagnostic tests for influenza, RSV and S. pneumoniae infections in the elderly, and subjects aged $\geq 18$ years with chronic cardiopulmonary conditions, or pneumonia / influenza type symptoms. in comparison to traditional laboratory culture.

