#### 5 STUDY POPULATION

#### 5.1 Study setting

This study will be done in three hospitals (Leicester Royal Infirmary, Glenfield Hospital, and Leicester General Hospital) that provide acute medical care for the University Hospitals of Leicester (UHL) Trust, Principally in the Medical Assessment Units. The UHL Trust serves a population of approximately 1 million subjects of all ages. The University Hospitals of Leicester NHS Trust is the only facility within the county of Leicestershire providing inpatient emergency medical care to the inhabitants of Leicestershire (population ~ 1 million). The laboratory tests will be carried out in the Molecular Diagnostic Laboratory, and Public Health Laboratory, Leicester Royal Infirmary. The study will carried out during the 36-month period August 1 2005- July 31 2008. Patient enrolment will occur during: September 1 2005 to June 30 2006; September 1 2006 to June 30 2007; & September 1 2007 to June 30 2008.

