#### 2. NASOPHARYNGEAL SPECIMENS

One (1) nasal, and one (1) nose and throat swab sample will be collected from all study participants. (See Appendix VIII) The nasal swab can be found in the The Quidel QuickVue Influenza A+B test kit, which is included in the sequentially numbered study packs. Similarly, nose and throat swabs for collection of nasopharyngeal specimens will be found in the participant's study pack. They will be used as follows:

• **GROUP 1 ONLY**: The swab in the Quidel QuickVue Influenza A+B test kit will be used in *one nostril only*, specifically to collect a nasal sample – for rapid near patient testing, in the MAU/ward, of participants in Group 1.

Patients randomised to Group 1 will have near patient tests for influenza A and B antigen done by the study nurse in an area of the MAU/ward where clinical tests such as urinalysis are done routinely. The instructions for collecting the Quidel QuickVue nasal sample and doing all tests are provided in Appendix IX. On completion of the test the Study nurse will:

- (a) Record the test result in the CRF;
- (b) Inform the team (i.e., the responsible nurse and/or doctor) that is providing clinical care of the patient of the rapid near patient test result (i) verbally; and (ii) by insertion of an adhesive label in the notes. The clinical team should be told that a negative test does not exclude infection with influenza A or B.
- (c) Document in the CRF the time that the team was informed, and who was told.
- **GROUPS 1, 2, and 3**: The nose and throat swabs for the molecular tests and traditional tissue culture studies (for influenza and RSV) will be used to swab the throat and *the opposite nostril* (i.e., ONE nostril only) to that used previously and placed in virus transport medium. The instructions for collecting the nose and throat sample are provided in Appendix VIII. The nose and throat sample will be collected from ALL study participants, specifically for:
  - Prompt, conventional viral culture (Groups 1, 2, and 3);
  - Prompt, rapid molecular testing for influenza A and B and RSV A and B (Group 2);
  - Deferred, molecular testing for influenza A and B and RSV A and B (Groups 1 and 3);
  - Deferred Quidel QuickVue test for influenza A and B (Groups 1 and 2)
  - Possible future tests for other respiratory pathogens of stored specimens, if tests for influenza, RSV, and *S. pneumoniae* are negative.

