#### 6.2.12 Convalescent serology (Day 10-90)

A 10ml convalescent blood sample will be collected from survivors at **10-90** days. The serum will be saved for paired acute and convalescent serology for influenza and RSV. The blood sample will be labelled with the participant's details, including name, date of birth, hospital number, and date of collection, AND in addition with the participant's unique trial code corresponding to the sequentially numbered study pack. The blood sample will be transported to the laboratory using the UHL transport system.

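### Section 9 dates the last batch testing and the combined three-year analysis before Year 3 enrolment and 28-day follow-up are over

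*Protocol*

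**What the plan says.** Three items in Protocol Section 9, Year 3, bear on this point.

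- Recruitment: "Sept 2007 to June 2008.: Year 3 clinical trial".
- The only laboratory slot in 2008, January to March, covers PCR, serology and "analysis of stored urine specimens from year 2 study; collate all data in preparation for analyses". Year 2 batch testing is already listed in the same section for summer 2007.
- The combined analysis, dated 1 April to 31 May 2008: "Data analysis (Years 1-3 combined); preparation of draft 3-year report". Section 9 dates nothing after 31 May 2008.

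Elsewhere, the synopsis and Section 5.1 give the third enrolment season as "September 1 2007 to June 30 2008" and the study period as ending on 31 July 2008. The synopsis adds: "All patients will be followed-up for 28 days". Section 7.1 still ends the third season on 1 March 2008.

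On testing, Section 6.1.14 makes PCR prompt in Group 2 and deferred in Groups 1 and 3. It makes the urine antigen test deferred in Group 3 only. Section 6.2.12 collects convalescent serum between day 10 and day 90. The synopsis (study design) and Section 4.1 state that every test will eventually be done on every patient.

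**The concern.** A combined analysis of three years cannot be complete while the third year is still recruiting, and Section 9 gives no later date on which it would be completed. A team working to these dates would leave out the last recruits, and many of those it included would not yet have 28-day deaths, costs or EuroQol scores.

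The laboratory dates raise a second question. PCR and the antigen test feed the definitions of influenza, RSV and pneumococcal positivity in Section 7.3. Those definitions select the patients for several endpoints in Section 7.5.1: time to no antibiotics, neuraminidase inhibitor use, infection-specific length of stay, and the isolation endpoints. If the deferred tests on late Year 3 samples were outstanding when the data were analysed, Group 2 patients would have PCR results and Group 1 and 3 patients would not. Group 3 would also lack antigen results. The infected subsets would then have been found by different tests in different groups.

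**Working it through.** **1. The protocol's own recruitment figure.** Section 7.1 uses 242 + 242 + 182 = 666 recruiting days. The unrounded rate of 11.57 elderly admissions per day is in the synopsis.

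666 × 11.57 = 7,705.6; × 5/7 = 5,504; × 2/3 = 3,669; × 3/4 = 2,752.

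The stated 2,752 is reproduced, so the sample-size calendar is the one that ends on 1 March 2008. The implied rate is 11.57 × 5/7 × 2/3 × 3/4 = 4.13 elderly recruits per calendar day.

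**2. The current enrolment calendar** (synopsis and Section 5.1, inclusive counts). The three seasons have 303 + 303 + 304 = 910 days.

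**3. Set against the analysis slot.**

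| Reference date | Enrolment days affected | Share of Year 3 | Share of all |
|---|---|---|---|
| Recruited 1 April to 30 June 2008 | 91 | 91/304 = 30% | 91/910 = 10% |
| 28 days not complete on 1 April (recruited after 4 March) | 118 | 39% | 13% |
| Still to be recruited after 31 May | 30 | 10% | 3% |
| 28 days not complete on 31 May (recruited after 3 May) | 58 | 19% | 6% |

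Of the 118 days in the second row, 118 − 91 = 27 (5 to 31 March) belong to patients already enrolled on 1 April but still in follow-up. The last two rows show that waiting until the slot closes does not remove the conflict.

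**4. In patients.** At a flat 4.13 per day, 91 × 4.13 = 376 elderly patients. The rate comes from September to April admissions, so only April (30 × 4.13 = 124) lies inside the source months. The other 61 days (61 × 4.13 = 252) are extrapolated, and the true number is probably lower.

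**5. Earliest complete dates.** 30 June 2008 + 28 days = 28 July 2008 for the last follow-up contact. Convalescent serum from the last recruit can be taken from about 10 July (day 10) to about 28 September (day 90).

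**6. Where the dates come from.** With the Section 7.1 end date, 1 March 2008 + 28 days = 29 March 2008, and an analysis opening on 1 April fits. With 30 June it does not. The season was lengthened, and the laboratory and analysis lines were not moved with it.

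**7. The laboratory slot.** Read literally, January to March 2008 repeats Year 2 work and no line names Year 3 samples. Read as Year 3, it still closes on 31 March with 91 enrolment days to come. In Years 1 and 2 batch testing was planned into August, after the season had closed, and was followed by a collation period to mid-December. Year 3 has neither.

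**The case against.** A reader might infer that the plan leaves Year 3 deferred tests undone and so builds group-dependent ascertainment into the infection endpoints. The document does not support that. The synopsis and Section 4.1 promise all tests on all patients, and Section 6.1.14 makes no exception for Year 3. The year label in the January to March 2008 line is very probably a misprint, because Year 2 testing is already listed for summer 2007 and the line leads directly into the combined analysis. A gap in a project timetable does not cancel the testing instructions. Bias between groups would arise only if the analysis went ahead before the outstanding tests were run. It would then touch the infection-defined subsets and diagnostic accuracy. All-patient comparisons such as length of stay would be incomplete but not biased between groups for this reason.

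A reader might also infer that late serum must fall after the 31 July 2008 study end. It need not: day 90 is the latest permitted date, and the last recruit can be sampled from about 10 July.

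Three further points are fair. The May 2008 product is called a draft, and a later final analysis is not excluded, although none is dated. The patient counts rest on a rate carried beyond its source months. Nor is a shortfall against 2,752 shown: at the same flat rate, the extended seasons to 31 March 2008 give (303 + 303 + 213) × 4.13, about 3,380 elderly patients.

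These points limit the consequences. They do not remove the conflict, which stands within Section 9 itself and against the synopsis and Section 5.1.

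**Conclusion.** The schedule is wrong as written. The combined analysis and the last laboratory slot belong to a season ending on 1 March 2008, while enrolment runs to 30 June and follow-up to about 28 July. Kept to the dates, the analysis would omit 91 of 910 enrolment days (10%; 30% of Year 3) and lack complete 28-day data for a further 27 days of recruits. The day counts rest only on dates in the protocol. The figure of about 376 elderly patients assumes that the September to April rate held through June, and is better read as an upper value. Group-dependent ascertainment of infection in late Year 3 recruits is a conditional risk, contrary to the protocol's own commitment, and not a stated feature of the plan. This should be corrected, but it does not call the design into question.

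**What to change.** Amend the timetable in Section 9:

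- Correct the year label in the January to March 2008 laboratory item from Year 2 to Year 3.
- Date a Year 3 run of deferred PCR, urine antigen and serology after enrolment closes, covering the samples from all groups.
- Place the combined Years 1 to 3 analysis after both the last day-28 contact and the last deferred test.
- Reconcile the synopsis, Section 5.1, Section 7.1 and Section 9 on the end of the third season.
- Check the day 10 to 90 serum window against the 31 July 2008 study end. Late recruits can be sampled early in the window, so neither date has to change for this reason alone.

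The cost is a timetable amendment and later reporting, by at least two to four months. From the end of the present analysis slot to the last day-28 contact is 58 days (31 May to 28 July), and from its start 118 days (1 April to 28 July), before any time for the deferred testing. Nothing in the design, the tests or patient care changes.
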